# 6 Trial design and setting

This trial is a longitudinal observational study of physical activity and physical fitness in 120 people with early-mid stage HD (assessed as having an overall low risk) with an additional nested evaluation of a 12-month physical activity intervention (n=30) compared to usual activity (n=30).

Participants will be recruited from current Enroll-HD sites in Europe and the USA. Enroll-HD is a worldwide research platform that has as its core a longitudinal observational study of HD families. Enroll-HD provides an infrastructure to support clinical studies such as the one proposed here. Recruitment for the longitudinal study and the nested RCT will be conducted over a period of 15 months, both with a 12 month follow up period. The trial is expected to last a total of 27 months. The end of the trial will be defined as last participant, last visit, which will be the 12-month assessment. This could be a participant in either the observational cohort or nested RCT.

All participants will undergo a baseline assessment as part of their annual Enroll-HD visit where standard measures will be collected as per the Enroll-HD study protocol. Additional assessments pertaining to physical activity will also be performed (see section 12.1 for further details). The additional assessments should be collected  $\pm$  4 weeks of the annual ENROLL visit. These assessments will be repeated after 12 months within  $\pm$  4 weeks of the next annual Enroll-HD visit. For those participants taking part in the nested RCT, an additional assessment will be performed at 6 months. For participants randomised to receive the physical activity and coaching intervention in the nested RCT, they will receive the intervention over a 12-month period which will include 18 home or site visits (pragmatically scheduled) and additional supportive monthly telephone calls.

All data will be entered directly into the trial database by local researchers via an individual log-in. Where data is obtained from third party sources exports will be obtained on a monthly basis for upload into the trial database.

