# 9 Recruitment, Screening, Registration and Randomisation

# 9.1 Participant identification and pre-screening

Participants will be identified from registered Enroll-HD participants at each site. If an individual is deemed suitable for PACE-HD and not yet recruited to Enroll, they could be recruited onto Enroll-HD at that time however must be enrolled on Enroll-HD prior to randomisation. Enroll-HD is a global research platform that has at its core a worldwide observational study for Huntington's disease families(https://www.enroll-hd.org/learn/about-this-study/). Enroll-HD monitors the onset of the disease and its progression in different people and open to the following categories: gene carriers, gene negative and family controls.

One of the optional components within the Enroll-HD study is the request to give permission to be contacted to receive information about other additional and affiliated HD research projects. In consenting to participate in the Enroll-HD study, participants also give their permission for their coded data to be made available to any researchers with a legitimate research project who wants to better understand HD. Only coded clinical data are shared with the researchers therefore, the risk that identifying information will be accidentally disclosed is low.

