# 9.5 Registration and Randomisation

# 9.5.1 Registration

Potential participants will be screened for eligibility by local site teams as described in section 9.1. Those meeting eligibility criteria and providing informed consent will be registered as a trial participant and assigned a unique trial identification number prior to baseline data collection. At sites conducting the nested RCT, the participant will then undergo a further safety assessment to determine their ability to take part safely in the interventional trial prior to baseline data collection. Only those passing the safety screening assessment will be eligible for randomisation. The Malnutrition Universal Screening Tool' ('MUST') for adults will be completed at baseline for those in the intervention sites.

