#### Physical Activity Monitoring

All participants will undergo physical activity monitoring following their baseline and 12 month assessments. Activity will be monitored using Gene-activ devices (which are worn like a wrist watch) for a period of 7 days. Participants will be required to return the Gene-activ device to the site co-ordinator after the monitoring period in a pre-paid, padded envelope provided. Gene-activ devices are not interactive and so the participant will remain blind to the data that is being recorded by the device.

Participants randomised to the intervention arm of the nested RCT will be provided with FitBit Charge 2 device as part of the intervention. These interactive devices will enable participants to track their physical activity and activity goals for the duration of the trial. Data from the FitBit devices will automatically sync to FitBit servers and summary data exports on defined parameters will be sent to the trial team. FitBit devices will not need to be returned at the conclusion of the trial.

Additionally, participants in both arms of the nested RCT will be asked to complete monthly diaries of physical activity. This can be an on-line option (prompted by text message delivery of a link to the online form) or a paper based option, dependent on the preference of the participant.

Traditionally, monthly activity data has been collected using a calendar format accessible on-line or on paper. However, completion rates of these formats is typically low. We have designed a novel electronic user interface for participants to provide activity data with the aim of improving completion rates. To test the validity and usefulness of the new design, participants recruited to the RCT arm will be randomised to receive a link to either the existing on-line diary or the novel electronic diary. The implementation of this will not affect activity at sites. A separate Study Within a Trial (SWAT) protocol will be written to define the objectives, outcome measures, randomisation, implementation and analysis of this study.

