# Data collection/assessments and blinding

All data will be collected by researchers at site and will include but is not limited to; local Enroll-HD coordinators, clinicians and physical therapists delivering the intervention. All assessments will be performed at the research site. Intervention delivery data will be collected at the point of intervention delivery, be that at the research site or participant's home, depending on the participant's preference. Due to the nature of the intervention and the pragmatic design of the nested RCT, researchers collecting assessment data will not be blind to the allocation of participants.

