# Nested RCT

Participants will be assessed at baseline, 6 months and 12 months.

Table 1: Assessments additional to the standard Enroll-HD test battery for all sites:

Construct	Measure	Time to complete	Time points
Fitness	Predicted VO2 Max will be measured during stepwise incremental exercise test  . The test is performed on a cycle ergometer with participants seated in a standardized position. Participants will attempt to maintain a cadence of 50 revolutions per minute (rpm), starting at 50 Watts and increasing by 25	20 min	Baseline, 6 months (RCT only), 12 months

	Watts every two minutes until test termination. The test will be terminated when the participant reaches volitional exhaustion or cadence drops by 10 rpm. At the end of each increment, work-rate (Watts), rating of perceived exertion (Borg RPE scale) and heart rate will be recorded for analysis and conversion to predicted VO2 max score.		
Walking endurance	The 6-minute walk test will be used as a measure of walking endurance. This test evaluates the distance walked over a 6 minute period, and has been validated for use in HD  .	10 min	Baseline, 6 months (RCT only) and 12 months
Patient- reported clinical symptoms	HD Pro-Triad  will be used to assess disease specific symptoms including cognitive decline, emotional/behavioural dyscontrol and motor dysfunction.	10 min	Baseline and 12 months
Physical Activity Monitoring	Brunel Lifestyle Physical Activity Questionnaire  self-report instrument that measures the planned and unplanned dimensions of lifestyle physical activity.	5 minutes	Baseline
	Research-grade physical activity monitors (Gene-activs) will be used for a 7-day physical activity assessment .  Participants will be given the monitors at the consent visit, and will be asked to return them at the baseline visit one week later. They will be requested to wear them for 24 hours a day for the full week, except when showering. Participants will be given the monitors at the end of the assessments, and will be given addressed stamped mailing envelopes to return the monitors one-week later. Data obtained for analysis will include level of overall physical activity, sedentary behavior and sleep patterns. For validation of sleep time compared to sedentary time, participants will be asked to complete and return sleep diaries for the 7 day period of physical activity assessment.	5 min	Baseline, 6 months (RCT only) and 12 months

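### The protocol contradicts itself on when the baseline 7-day activity week is worn, and does not require that week to end before randomisation

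*Protocol*

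**What the plan says.** **Timing of the activity week.** Section 12, Physical Activity Monitoring, puts it after the visit: "All participants will undergo physical activity monitoring following their baseline and 12 month assessments". Wear lasts 7 days and the device goes back in a pre-paid envelope.

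Table 1 (section 12.1) gives two instructions in one cell. The first puts the week before the visit: "Participants will be given the monitors at the consent visit, and will be asked to return them at the baseline visit one week later". The second puts it after: "Participants will be given the monitors at the end of the assessments, and will be given addressed stamped mailing envelopes". Neither is limited to a particular time point, and the row covers baseline, 6 months (RCT only) and 12 months.

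**Timing of randomisation and intervention.** Table 3 marks the baseline measures, randomisation, first delivery of the intervention, text prompts and FitBit monitoring in the same month-1 column, without an order among them.

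**Conditions for randomisation.** Section 9.5.1 places registration and the safety screen before baseline data collection and then says "Only those passing the safety screening assessment will be eligible for randomisation". Section 9.1 adds that a participant "must be enrolled on Enroll-HD prior to randomisation". No other condition is stated.

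**Link to Enroll-HD.** Section 6 says "All participants will undergo a baseline assessment as part of their annual Enroll-HD visit", with the additional assessments allowed within plus or minus "4 weeks of the annual ENROLL visit". The UHDRS total motor score is a minimisation factor (sections 9.5.2 and 14.1).

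**Blinding.** Section 12 states that "researchers collecting assessment data will not be blind to the allocation of participants". Section 14.2 says participants are not blinded either.

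**The concern.** Seven-day activity is a named secondary outcome and is also the behaviour that the intervention sets out to change. A baseline value is useful only if it precedes allocation. A site that follows section 12 can randomise at or just after the baseline visit, issue a FitBit, begin coaching, and record the baseline Gene-activ week while all of this is under way. A site that follows Table 1's first instruction records the week beforehand. Both comply with the protocol.

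Two things are at stake. The baseline value may already contain some early response to the intervention, or a reaction to knowing the allocation. It may also differ in meaning from site to site. Analysis cannot recover a pre-treatment week that was never recorded, so this cannot be left to the statistical analysis plan. If the IPAQ, which also asks about the last 7 days and is meant to validate the monitor, is timed to the same week, it shares the problem.

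**Working it through.** The document gives no figure on this point to reproduce. Its one sample-size figure, a half-width of 8.2% for 70% retention in 120 participants, is correct (1.96 × √(0.7 × 0.3 / 120) = 0.0820) but has no bearing here.

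**Step 1: set the places side by side.**

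| Place | When the baseline week is worn | Relation to randomisation |
|---|---|---|
| Section 12, Physical Activity Monitoring | After the baseline assessment | Not stated |
| Table 1, first instruction | Consent visit to baseline visit | Before the baseline visit ends |
| Table 1, second instruction | After the assessments | Not stated |
| Table 3 | Month-1 column | Same column as randomisation and first intervention delivery |
| Sections 9.1 and 9.5.1 | Not mentioned | Only Enroll-HD enrolment and the safety screen are required |

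Section 12 and Table 1's first instruction cannot both hold at baseline. Nothing in the other rows excludes a wear week after allocation.

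**Step 2: which analyses would be affected.** Section 15.1 compares the arms with linear models that control for the factors used to balance the randomisation. Section 9.5.2 lists these as age, gender and total motor score. Baseline accelerometry is not among them, and no change score is specified. A comparison of 6- or 12-month activity under that model does not use the baseline week, so a late week does not bias it.

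**Step 3: what a late week would do if the baseline were used.** Let δ be the true effect at follow-up and f the share of δ already present as a between-arm difference in the baseline week. Let ρ be the within-arm correlation of baseline with follow-up. Assume equal standard deviations at the two times, so that the regression slope on baseline equals ρ.

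- Change score: δ − fδ = δ(1 − f).
- Baseline-adjusted estimate: δ − ρ·fδ = δ(1 − ρf).

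Share of the true effect retained:

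| f (assumed) | Change score | Adjusted, ρ = 0.5 | Adjusted, ρ = 0.7 |
|---|---|---|---|
| 0 | 100% | 100% | 100% |
| 0.10 | 90% | 95% | 93% |
| 0.25 | 75% | 87.5% | 82.5% |
| 0.50 | 50% | 75% | 65% |

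Neither f nor ρ is in the document. The table shows how the bias behaves and is not an estimate of it.

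**Step 4: the Enroll-HD baseline.** The window in section 6 allows the additional assessments up to 4 weeks before the annual visit, which is 4/52 = 7.7% of the 12-month intervention period. It does not set the date of randomisation. Minimisation needs a total motor score, so some value must exist at allocation. The protocol does not say whether that value comes from the current visit or an earlier one, or whether the same value is the model covariate.

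**The case against.** **Table 1 has a natural reading.** The consent-visit rule can be taken to govern baseline and the hand-out after the assessments to govern follow-up; section 18 describes such a post-intervention week. This is plausible, and the fix adopts it. But the table does not say so, and section 12 still contradicts it for baseline.

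**After the baseline assessment is not after randomisation.** No section says that randomisation happens at the baseline visit. The shared Table 3 column is on a scale of months and gives no order within the month. Section 14.1 also refers to a separate randomisation schedule, not shown here, which may fix the order. This stands: late recording is permitted, not established. A reader might infer that treatment does contaminate the baseline of all 60 RCT participants. The protocol does not support that. All 60 are exposed to the ambiguity, only about 30 receive the intervention, and a site may finish the week before randomising.

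**A large bias is not shown.** A reader might take the lower rows of the second table as the likely loss. Nothing in the document suggests that a quarter or half of a 12-month effect appears in the first week. The programme is 18 sessions whose timing the participant settles with the coach, and the stated model uses neither a change score nor baseline activity. This stands in full.

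**The Enroll-HD baseline is better protected.** A reader might infer that baseline motor, cognitive and functional scores are also collected after randomisation. Section 6 makes baseline part of the annual visit, and section 14.1 speaks of balancing motor impairment at baseline. What remains is a narrower question: which motor score is used.

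**Blinding adds little on the measurement side.** Gene-activ is a device whose data participants cannot see. That is right for how activity is measured, but knowing the allocation can still change how active someone is that week.

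**Conclusion.** The contradiction over the baseline wear week is real, and no stated rule requires the week to end before randomisation. For RCT participants, baseline activity can therefore be recorded after an unblinded allocation and after the intervention starts, and it can differ in meaning between sites.

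The consequence is limited. The stated follow-up contrast is unbiased by a late wear week, provided the motor score in the model predates randomisation. The harm falls on the description of pre-treatment activity and on any change-from-baseline or baseline-adjusted analysis of activity that is later adopted. Its size cannot be derived from the document and may be zero.

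The primary objective is feasibility, no formal hypothesis tests are planned, and activity is one of many exploratory secondary outcomes. This is a cheap improvement that should be made. It does not undermine the trial's main purpose.

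**What to change.** 1. Reconcile section 12 (Physical Activity Monitoring), Table 1 and Table 3. For RCT participants, state that the baseline Gene-activ week runs from the consent visit to the baseline visit, and that it and the other PACE-HD baseline measures are completed before randomisation.
2. Limit the hand-out at the end of the assessments to follow-up visits.
3. Add a database check that compares the end of the wear week and the baseline assessment dates with the randomisation date. The condition should be that the week has ended, not that the recording is valid, so that a device failure does not block randomisation.
4. State that the UHDRS total motor score used for minimisation and as a covariate is one dated before randomisation.
5. Flag baseline items dated after randomisation, but do not set them to missing. Section 15.1 specifies a complete-case analysis with the balancing factors as covariates, so a motor score set to missing would drop that participant from every adjusted model.

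The cost is wording and one date check. Randomisation may move by about a week for some participants, mainly where consent and baseline assessment would otherwise fall together.

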# Data collection/assessments and blinding

All data will be collected by researchers at site and will include but is not limited to; local Enroll-HD coordinators, clinicians and physical therapists delivering the intervention. All assessments will be performed at the research site. Intervention delivery data will be collected at the point of intervention delivery, be that at the research site or participant's home, depending on the participant's preference. Due to the nature of the intervention and the pragmatic design of the nested RCT, researchers collecting assessment data will not be blind to the allocation of participants.

# Process Evaluation:

The process evaluation will utilise qualitative data (semi-structured interviews with intervention staff) and quantitative data (structured reflections by members of the research team delivering the intervention and a purpose developed fidelity questionnaire as well as data on completed visits) to assess fidelity (whether the intervention has been delivered as intended and as a measure of quality assurance), and the key mechanisms of change. Participants and their care-givers will be asked to complete a structured questionnaire that focusses on their views of the trial and of the intervention.

We will also attempt to contact any participants who drop out of the intervention to ascertain reasons for discontinuing.

#### 12.1 Assessments

As previously described, we will utilize assessments from the standard Enroll-HD battery. The full Enroll-HD protocol can be found at https://www.enroll-hd.org/enrollhd\_documents/Enroll-HD-Protocol\_1.0.pdf. In addition to the data gathered as part of the Enroll-HD battery we will collect a number of supplementary measures which are detailed in Tables 1 and 2. Sites must ensure that they conduct the follow up assessment of supplementary measures to coincide with the annual ENROLL-HD visit (± 4 weeks). The full participant schedule of enrolment, assessment and interventions can be found in Table 3

# Longitudinal Observational Study

Participants will be assessed at baseline and again at 12 months

# Nested RCT

Participants will be assessed at baseline, 6 months and 12 months.

Table 1: Assessments additional to the standard Enroll-HD test battery for all sites:

Construct	Measure	Time to complete	Time points
Fitness	Predicted VO2 Max will be measured during stepwise incremental exercise test  . The test is performed on a cycle ergometer with participants seated in a standardized position. Participants will attempt to maintain a cadence of 50 revolutions per minute (rpm), starting at 50 Watts and increasing by 25	20 min	Baseline, 6 months (RCT only), 12 months

	Watts every two minutes until test termination. The test will be terminated when the participant reaches volitional exhaustion or cadence drops by 10 rpm. At the end of each increment, work-rate (Watts), rating of perceived exertion (Borg RPE scale) and heart rate will be recorded for analysis and conversion to predicted VO2 max score.		
Walking endurance	The 6-minute walk test will be used as a measure of walking endurance. This test evaluates the distance walked over a 6 minute period, and has been validated for use in HD  .	10 min	Baseline, 6 months (RCT only) and 12 months
Patient- reported clinical symptoms	HD Pro-Triad  will be used to assess disease specific symptoms including cognitive decline, emotional/behavioural dyscontrol and motor dysfunction.	10 min	Baseline and 12 months
Physical Activity Monitoring	Brunel Lifestyle Physical Activity Questionnaire  self-report instrument that measures the planned and unplanned dimensions of lifestyle physical activity.	5 minutes	Baseline
	Research-grade physical activity monitors (Gene-activs) will be used for a 7-day physical activity assessment .  Participants will be given the monitors at the consent visit, and will be asked to return them at the baseline visit one week later. They will be requested to wear them for 24 hours a day for the full week, except when showering. Participants will be given the monitors at the end of the assessments, and will be given addressed stamped mailing envelopes to return the monitors one-week later. Data obtained for analysis will include level of overall physical activity, sedentary behavior and sleep patterns. For validation of sleep time compared to sedentary time, participants will be asked to complete and return sleep diaries for the 7 day period of physical activity assessment.	5 min	Baseline, 6 months (RCT only) and 12 months
	International Physical Activity Questionnaire (Short Form) will be used to assess 7-day physical activity, and to validate with the physical activity monitors. 	5 min	Baseline, 6 months (RCT only) and 12 months

Table 2: Assessments additional to the standard Enroll-HD test battery for RCT sites only

Construct	Measure	Time to complete	Time points
Motor and dual task function	The Clinch Token Transfer Test (C3T) is a dual-task assessment of bilateral, upper motor function that consists of three-coin transfer tasks which increase in difficulty (baseline simple, baseline complex and a dual task). The time taken to pick up and transfer the coins from dominant to non-dominant hand and	b	Baseline and 6 months

	place into a purpose developed box is recorded. The addition of cognitive load increases the task complexity.		
Motor Function	Q-motor was developed in TRACK-HD and TRACK-ON-HD where motor tasks are related to functionally relevant everyday tasks. All Q-Motor assessments are based on the application of pre-calibrated and temperature controlled force transducers and 3D position sensors with very high sensitivity and test-retest reliability across sessions and sites in a multicenter clinical trial.	10 min	Baseline and 12 months
Cognitive Function	Q-Cog was developed in TRACK-HD and TRACK-ON-HD where cognitive tasks are related to functionally relevant everyday tasks. Q-Cog assessments deploy the technology used in the Q-Motor system to benefit from the high accuracy of the sensors in tasks with high cognitive load. Again this offers high sensitivity and test-retest reliability across sessions and sites in a multicenter clinical trial.	20 min	Baseline and 12 months
Self- efficacy	The Lorig Self Efficacy  scale will be utilized to measure self-efficacy related to exercise (exercise sub-scale only)	5 min	Baseline, 6 months and 12 months

Table 3. Schedule of enrolment, interventions and assessments (from HRA CTIMP protocol template)

	Screening Baseline			Intervention	Follow Up	
IMEPOINT** (months)	minus 4 weeks to 0	1	Months 2-6	Month 6	Months 7-12	Month 12
NROLMENT (OBSERVATIONAL SITES)	11001111111					
Pre-screening from ENROLL-HD	x					
ligibility screen (records review)	x					
nformed consent		х				
Registration	+	x				
0						
MBEDDED RCT (3 SITES)	v					
Pre-screening from ENROLL-HD	X					
Eligibility screen (records review)		х	_			_
MUST malnutrition universal screening tool	X		-			
nformed consent	X	×	-			
Physical Activity Readiness Quesionnaire (Par-Q) safety screening	-	х				
Registration		X			-	
Randomisation		Х				
INKED ENROLL-HD DATA (ALL SITES)						
Age		х				
ocal CAG high value		х				
Date of HD clinical diagnosis		х				
Ethnicity		х				
Gender		х				
Height		X				
Neight		×				×
	-	×				×
BMI	+	X				×
Medications	_		-		_	
Comorbidities	_	Х		_		X
Pharmacotherapy		х	-		-	X
Non-Pharmacologic Therapies		X				×
JHDRS TMS		х				X
UHDRS TFC		x				x
UHDRS Independence scale		х				х
UHDRS Function Assessment		x				х
Symbol Digit Modality test (numbers correct)		х				х
Verbal fluency category		х			1	x
		×	-		+	×
Letter Fluency	_	x			1	×
Trailmaking	_		_		1	x
Stroop word reading test		×	-	-	-	
Strrop colour naming		X		-	1	X
Stroop Interference		X			ļ	×
CSRI		X				X
HADS-SIS		X				X
Problem Behaviours Assessment (apathy sub domain)		х				х
SF12		х				х
TUG		х				х
30 sec chair stand		x				x
Medication changes since last visit		×	1			x
Event Reporting		-	_	1		x
PACE-HD STUDY DATA (ALL SITES)		u u				×
Physical Fitness predicted VO2		X	_	-		_
6 minute walk test	_	X		-		X
HD Pro Triad		х	-	-		X
Brunel lifestyle physical activity questionnaire		х				-
7 day accelerometer based physical activity assessment with sleep diary (debrief		×				×
interview over phone)		+				×
Self reported physical activity (iPAQ short last 7 days, telephone format)	_	×	+			-
Event Reporting						
PACE-HD STUDY DATA (RCT ONLY)						
Physical Fitness predicted VO2		Х		X		Х
7 day accelerometer based physical activity assessment with sleep diary (debrief						·
interview over phone)		Х		х	-	X
Self reported physical activity (IPAQ short last 7 days, telephone format)		X		х		Х
C3T		Х		х		
Q Motor assessment battery		×				х
Q Cog assessment battery		х				х
Lorig Self Efficacy Scale (exercise domain)		X		х		х
PHYSICAL INTERVENTION						
		×	XXXX		XXXX	
Delivery of physical intervention (home visits)	_	_		_	XXXX	
Text messaging prompts		X	XXXX	+		1
Activity monitoring data to record adherence to intervention (FitBit activity data)		Х	X	-	X	-
Telephone review (Health and Falls Record)		х	X	X	х	-
Adverse event assessments		X	х	х	х	x
USUAL CARE						V
Telephone review (Health and Falls Record)		x	х	х	х	
						-

